6.5 TREATMENT COMPLIANCE

The Investigator is ultimately responsible for supervising compliance with the instructions described in this study protocol.

7. STUDY EVALUATIONS

7.1 EFFICACY

7.1.1 Test for COVID-19

A SARS-CoV-2 Rapid Antigen Test, provided by the Sponsor, will also be performed at the site by the research team on Day 4 until discharge, and always at Days 1, 4 (± 1 day), 8 (± 1 day), 15 (± 1 day), 30 (± 2 days), 45 (± 2 days), and 60 (± 3 days); if RAT is positive at discharge, RAT should also be monitored on a weekly basis until negative. A negative result should be confirmed with a second RAT within 48 h, by the investigator team.

Quantitative PCR to assess viral load on Day 1 before initiation of treatment and on Days 4 (± 1 day), 8 (± 1 day), 15 (± 1 day), 30 (± 2 days), 45 (± 2 days), and 60 (± 3 days) (see [Appendix 13 - Schedule of Assessments and Procedures](#)), will be performed by a central laboratory. Based on these assessments, changes in viral load respect to Day 1 will be calculated for each patient. The proportion of patients with either $> 2 \log 10$ reductions or undetectable SARS-CoV-2 on each time point will also be assessed.

Details regarding the collection, processing, storage, and shipment of oro-nasopharyngeal samples for qPCR testing will be provided to each investigational site before initiation of the study in the form of a laboratory manual. All oro-nasopharyngeal samples for qPCR must be

processed and shipped as specified in the laboratory manual to maintain sample integrity. Any deviations from the processing steps (e.g., sample collection and processing steps, interim storage, or shipping conditions), including any actions taken, must be documented and reported to the Sponsor. On a case-by-case basis, the Sponsor may make a determination as to whether sample integrity has been compromised. Any deviation from the specified sample handling procedure that results in compromised sample integrity will be considered a protocol deviation.

Samples will be analysed using validated analytical methods, as approved by the Sponsor.

7.1.2 Chest Imaging

Chest radiograph abnormalities will be detected by chest X-ray on Day 1, 15 (± 1 day), and 30 (± 2 days) and submitted to central review. Chest imaging performed within 48 hours of Day 1 is accepted and does not have to be repeated. Images will be reviewed for the presence of pulmonary infiltrates, pleural fluid, atelectasis, pulmonary oedema, and other findings and scored using Brixia criteria (86).

7.1.3 Clinical Status

Clinical status (including the need for oxygen supplementation) will be assessed at least once a day, or whenever it changes, while receiving hospital care and on Days 4 (± 1 day), 8 (± 1 day), 15 (± 1 day), 30 (± 2 days), 45 (± 2 days) and 60 (± 3 days), using the 11-point WHO Clinical Progression Scale ([Appendix 1 – 11-Point World Health Organization \(WHO\) Clinical Progression Scale](#)).

COVID-19 signs or symptoms will be systematically collected and scored according to a check list ([Appendix 10 - COVID-19 signs/symptoms checklist](#)) together with the WHO Clinical Status. Research team will record a daily severity rating of their symptom severity over the past 24 hours based on NCI-CTCAE v5.0 criteria. Sense of smell and sense of taste will each be rated on a 3-point Likert scale where: “0” is reported if the sense of smell/taste was the same as usual, “1” if the sense of smell/taste was less than usual, and “2” for no sense of smell/taste.

Sustained improvement of all targeted COVID-19 signs/symptoms is defined as the event occurring on the first of 4 consecutive days when all symptoms scored as NCI-CTCAE category of moderate-severe intensity, or requiring medical intervention, or limiting instrumental ADL (see [Appendix 10 – COVID-19 signs/symptoms checklist](#)) are scored as mild or absent AND all symptoms scored mild or 0 (absent) at study entry are scored as 0.

The first day of the 4 consecutive-day period will be considered the First Event Date.

Sustained resolution is defined as when all targeted symptoms are scored as 0 for 4 consecutive days. The first day of the 4 consecutive-day period will be considered the First Event Date.

For any symptoms not present at baseline, it must be absent at Day 30 (+/-2) to be counted as sustained alleviation/resolution.

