EFFICACY EVALUATION CRITERIA	
Efficacy parameters include:
 
 • Mortality (all-cause and related to COVID-19); • COVID-19 signs and symptoms will be collected daily from Day 1 until the end of hospital care; thereafter at Days 4, 8 (±1), 15 (±1), 30 (±2), 45 (±2), and 60 (±3); • Clinical status is assessed using the WHO 11-point Clinical Progression Scale; • Lung function tests include fraction of inspired oxygen (FiO₂) (%), oxygen saturation (SpO₂), partial pressure of oxygen (PaO₂) (mmHg) [could be imputed from oxygen saturation (SpO₂)]. PaO₂/FiO₂ ratio will also be calculated (See Appendix 5 - Imputation of PaO₂/FiO₂ ratio); • SARS-CoV-2 quantitative real-time-reverse transcription polymerase chain reaction test (qRT-PCR) will be performed by central laboratory from oro-nasopharyngeal exudates on Day 1 before administration of the study drug and repeated at Days 4 (±1), 8 (±1), 15 (±1), 30 (±2), 45 (±2), and 60 (±3). Name of the variant will be collected if known; • SARS-CoV-2 Rapid Antigen test (RAT) will be performed every other day from Day 4 until discharge, and always at Days 1, 4 (±1), 8 (±1), 15 (±1), 30 (±2), 45 (±2), and 60 (±3); if RAT is positive at discharge, RAT should also be monitored on a weekly basis until negative. A

	
negative result should be confirmed with a second RAT within 48 h, by the investigator team;
 
 • Humoral response anti-SARS-CoV-2; • T-cell response against SARS-CoV-2; • Additional therapies for COVID-19; • Type and dates of oxygen support; • Radiological scores (chest X-ray, Brixia score; centrally assessed) (See Appendix 9 – Brixia Score); • Death date and reason; • Dates of discharge from ICU or hospital, and date of eventual re-admission; • Inflammatory and immunological biomarkers, including C-reactive protein (CRP), procalcitonin, lactate dehydrogenase (LDH), ferritin, neutrophil-to-lymphocyte ratio, ALC, D-Dimer, and multiplex cytokines assay; • Compliance with scheduled therapies for the underlying disease.
PHARMACOKINETIC (PK) EVALUATIONS	
PK analysis of plitidepsin concentration-time data will be performed in 30 patients using non-linear mixed-effects modelling. Individual PK parameters will be (See Section 7.6):
 
 • Plasma total area under the curve (AUC). • Plasma total clearance (CL).

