4.1 INCLUSION CRITERIA

To be eligible for inclusion into this study, each patient must fulfil the following inclusion criteria within 48 hours prior to randomisation:

General inclusion criteria:

1. Signed informed consent obtained prior to initiation of any study-specific procedures and study treatment;
2. Patient aged ≥ 18 years;
3. Patient diagnosed COVID-19, with the following characteristics: a) A regulatory approved test, collected no more than 3 days prior to study randomisation, with either a Ct value ≤ 30 or a positive antigen test;
b) Presence of any of the selected signs/symptom listed in [Appendix 10 - COVID-19 signs/symptoms checklist](#) within the last 24 h;

4. Patient already admitted or requiring hospital care* for symptomatic COVID-19, for which at least one antiviral has failed[†] or cannot be used[‡], after a minimum washout period of 24h for small molecules (e.g., remdesivir, molnupiravir, nirmaltrevir/ritonavir) and 5 days for antiviral monoclonal antibodies (e.g., tixagevimab + cilgavimab) or convalescent plasma.

* The definition of hospital care is based on the need to use a hospital environment (hospital ward, day hospital) for treatment administration and/or clinical monitoring of the patient with COVID-19.

[†] Failure of a prior antiviral is defined as a documented lack of clinical response, plus evidence of persisting positivity for SARS-CoV-2 in an appropriate biological sample, determined by a regulatory approved test, collected no more than 3 days prior to study randomisation, with either a Ct value ≤ 30 (RT-PCR) or a positive antigen test.

[‡] Contraindication, absence of labelled indication, guidelines, or drug unavailability.

5. Adequate bone marrow, liver, kidney, and metabolic function, defined by the following tests performed at local laboratory:
 - Absolute neutrophil count $\geq 500/\text{mm}^3$ ($0.5 \times 10^9/\text{L}$);
 - Platelet count $\geq 50\,000/\text{mm}^3$ ($50 \times 10^9/\text{L}$);
 - Alanine transaminase (ALT) $\leq 3 \times$ upper limit of normal (ULN) ($\leq 5 \times$ ULN if pre-existent liver involvement by the underlying disease);
 - Serum bilirubin $\leq 1.5 \times$ ULN (or direct bilirubin $< 1.5 \times$ ULN when total bilirubin is above ULN);
 - Estimated glomerular filtration rate $\geq 30 \text{ mL/min}$ [CKD-EPI Creatinine Equation (2021)] (85).

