5.7 EVALUATIONS AND PROCEDURES DURING TREATMENT

	ASSESSMENT/PROCEDURES	TIME
Clinical evaluation	
 COVID-19-related signs and symptoms checklist (Appendix 10 – COVID-19 signs/symptoms checklist). Clinical status (11-point WHO Clinical Progression Scale). Vital signs will include body temperature (°C), SBP (mmHg), DBP (mmHg), pulse rate (bpm) and respiratory rate (breaths/min). Targeted physical examination. A targeted physical examination will include heart, lungs, abdomen, extremities plus central nervous system (CNS) assessment, based on the investigator's decision as per clinical evolution. Lung function tests include PaO₂, FiO₂ and SpO₂. PaO₂/FiO₂ ratio will also be measured; either Ellis or Rice formulae can be used to estimate PaO₂/FiO₂ ratio (Appendix 5 - Imputation of PaO₂/FiO₂ ratio). 	Days 1, 2, 3, 4 (± 1). When applicable, these assessments should be performed before treatment administration.

	ASSESSMENT/PROCEDURES	TIME
	
 • Concomitant therapies. • Subsequent medications for SARS-CoV-2 infection. • Subsequent medications for the underlying disease. 	Days 1, 2, 3, 4.
Laboratory tests*	Haematology: haematocrit, red blood cells (RBC), differential WBC counts (including neutrophil and lymphocyte counts), platelet count and haemoglobin (See Appendix 8 – Clinical Laboratory Analyses).	Days 1, 4 (± 1), and whenever clinically indicated for an AE evaluation. When applicable, these assessments should be performed before treatment administration.
	Biochemistry: Liver function test [ALT, AP, AST [†] , albumin, total bilirubin (direct bilirubin if total is abnormally elevated)], lactate dehydrogenase (LDH), glucose [fasting], sodium, potassium, calcium, BUN/urea, gamma glutamyl transferase (GGT), creatinine, calculated creatine clearance [CKD-EPI], creatine phosphokinase (CPK), amylase, lipase, procalcitonin, ferritin, and CRP (See Appendix 8 – Clinical Laboratory Analyses).	Days 1, 4 (± 1), and whenever clinically indicated for an AE evaluation. When applicable, these assessments should be performed before treatment administration.
	Coagulation: D-Dimer (See Appendix 8 – Clinical Laboratory Analyses).	Day 1, 4 (± 1), and whenever clinically indicated for AE evaluation. When applicable, these assessments should be performed before treatment administration.
	Urine analysis (semi-quantitative elemental tests	Day 1 (previous to treatment administration). Repeat whenever

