5.8 EVALUATIONS DURING FOLLOW-UP

	ASSESSMENT/PROCEDURES	TIME
Clinical evaluation	
 COVID-19-related signs and symptoms checklist (Appendix 10 – COVID-19 signs/symptoms checklist). 	Daily while admitted, upon discharge, Day 8 ± 1 Day 15 ± 1 Day 30 ± 2 Day 45 [¥] ± 2 and if readmission.

ASSESSMENT/PROCEDURES	TIME

 Clinical status (11-point WHO Clinical Progression Scale) Vital signs will include body temperature (°C), SBP (mmHg), DBP (mmHg), pulse rate (bpm) and respiratory rate (breaths/min). Targeted physical examination. A targeted physical examination will include heart, lungs, abdomen, extremities plus CNS assessment, based on the investigator's decision as per clinical evolution. Lung function tests include PaO₂, FiO₂ and SpO₂. PaO₂/FiO₂ ratio will also be measured; either Ellis or Rice formulae can be used to estimate PaO₂/FiO₂ ratio (Appendix 5 - Imputation of PaO₂/FiO₂ ratio). 	*Only assessment of COVID-19-related signs and symptoms checklist

 Concomitant therapies. Subsequent medications for SARS CoV 2 infection. Subsequent medications for the underlying disease. 	Throughout follow-up period, if changes
Laboratory tests*	Haematology: haematocrit, RBC, differential WBC counts

	ASSESSMENT/PROCEDURES	TIME
	(including neutrophil and lymphocyte counts), platelet count and haemoglobin (See Appendix 8 – Clinical Laboratory Analyses).	Day 15 ± 1 Day 30 ± 2 If clinically indicated (AE), and if readmission
	Biochemistry: Liver function test [ALT, AP, AST [†] , albumin, total bilirubin (direct bilirubin if total is abnormally elevated)], LDH, glucose [fasting], sodium, potassium, calcium, BUN/urea, GGT, creatinine, calculated creatine clearance [CKD-EPI], CPK, amylase, lipase, procalcitonin, ferritin, and CRP (See Appendix 8 – Clinical Laboratory Analyses).	
	Coagulation: D-Dimer (See Appendix 8 – Clinical Laboratory Analyses).	
	Urine analysis (semi-quantitative elemental tests for specific gravity, blood, pH, proteins, bilirubin, glucose, ketones, nitrites, and qualitative analysis of the sediment).	Repeat whenever clinically indicated for AE evaluation.
Inflammatory and immunological biomarkers in blood (central laboratory)	Luminex® Multiplex cytokine assessment.	Day 8 ± 1 Day 15 ± 1 Day 30 ± 2
Anti-SARS-CoV-2 (central laboratory)	IgG/M anti-protein S and N.	Day 30 ± 2
	T-cell response (IFN- γ) to SARS-CoV-2 S-protein (Quantiferon®).	

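### Sustained improvement and resolution need four consecutive daily symptom scores, but daily scoring is scheduled only until hospital care ends, and the censoring rule does not allow for this

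*Protocol*

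**What the plan says.** **Definition.** Protocol 7.1.3 states: "Sustained improvement of all targeted COVID-19 signs/symptoms is defined as the event occurring on the first of 4 consecutive days" (the remaining conditions concern the symptom grades). It also states: "Sustained resolution is defined as when all targeted symptoms are scored as 0 for 4 consecutive days". Both events are dated to the first day of the run. For symptoms that were absent at baseline there is one further condition: "it must be absent at Day 30 (+/-2) to be counted as sustained alleviation/resolution".

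**Collection.** The Synopsis (efficacy evaluation criteria) states: "COVID-19 signs and symptoms will be collected daily from Day 1 until the end of hospital care". After that it lists Days 4, 8, 15, 30, 45 and 60. Protocol 5.7 gives the treatment-period checklist days: "Days 1, 2, 3, 4 (± 1). When applicable, these assessments should be performed before treatment administration". Protocol 5.8 has "Daily while admitted, upon discharge", followed by Days 8, 15, 30 and 45 and readmission. Protocol 5.9 adds Day 60. One sentence in 7.1.3 has no stated end: "Research team will record a daily severity rating of their symptom severity over the past 24 hours".

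**Hospital care.** Inclusion criterion 4 (Protocol 4.1) defines hospital care by "the need to use a hospital environment (hospital ward, day hospital) for treatment administration and/or clinical monitoring".

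**Analysis.** SAP 11.8, Table 3, takes over the Protocol 7.1.3 definition and plans an unstratified Kaplan-Meier analysis in the FAS. SAP 9.0 allows no imputation or carry-forward unless noted. It censors patients without an event at their last valid assessment before end of study. No rule is specific to this endpoint, and none builds a four-day run from isolated visits.

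**The concern.** The definition needs a score on each of four successive days. Once daily scoring stops, the remaining visits are too far apart to supply such a run. A patient who improves and goes home the next day will usually have no recordable event, however lasting the improvement.

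The censoring rule then matters. If a single visit on Day 45 or Day 60 counts as the last valid assessment, that patient stays in the risk set as not improved for weeks in which the event could not have been observed. The curve then reflects the time between improving and leaving care as well as the time to improvement. Two programmers could both follow SAP 9.0 and draw materially different curves. Patients with short care, including day-hospital care, are the clearest case, because almost no window is left in which an event can be recorded.

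**Working it through.** The plan gives no figure for this endpoint, so there is nothing to reproduce. The check has two parts: what the schedule allows, and how much the censoring day could matter under stated assumptions.

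**1. What the schedule allows**

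Let D be the last day of daily scoring. An event dated to day s needs scores on s, s+1, s+2 and s+3.

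- With daily scores only, s + 3 ≤ D, so the latest recordable start is D − 3.
- If a scheduled visit falls on day D + 1, the limit becomes D − 2.

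The enumeration below uses the Synopsis and Protocol 5.7-5.9 schedules, with the visits at nominal dates and at the most favourable dates inside their windows.

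| Last daily score | Latest start, nominal visits | Latest start, best placement |
|---|---|---|
| Day 4 | Day 1 | Day 2 |
| Day 6 | Day 3 | Day 4 |
| Day 9 | Day 6 | Day 6 |
| Day 12 | Day 9 | Day 9 |
| Day 13 | Day 10 | Day 11 |

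For discharge on Day 5 or later, no placement of visits gave a run starting on or after discharge. If care ends on Day 3, the only recordable start is Day 1. There is none if the Day 4 visit is held on Day 3 or Day 5, as the ±1 window in Protocol 5.7 permits; the Synopsis lists Day 4 for symptoms without a window. Readmission restarts daily scoring.

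**2. How much the censoring day could matter**

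The documents do not give the gap between improvement and end of care, so everything here is assumed:

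- improvement day is lognormal, median 7, log-SD 0.6, rounded up;
- end of care is improvement day plus a Normal gap with SD 3 days, not before Day 4;
- visits are uniform within their windows;
- improvement lasts and nobody dies;
- 40,000 simulated patients per scenario.

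Kaplan-Meier percentage improved by Day 30 (true value 99.2%):

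| Non-events censored at | Gap 3 | Gap 4 | Gap 5 | Gap 6 | Gap 7 | Gap 8 |
|---|---|---|---|---|---|---|
| Day 60 visit | 58.6 | 70.4 | 80.3 | 88.2 | 93.2 | 96.3 |
| Discharge | 92.6 | 95.8 | 97.5 | 98.4 | 98.9 | 99.1 |
| Last evaluable start day | 96.0 | 97.5 | 98.3 | 98.8 | 99.0 | 99.1 |

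By Day 15 (true value 90.2%):

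| Non-events censored at | Gap 3 | Gap 4 | Gap 5 | Gap 6 | Gap 7 | Gap 8 |
|---|---|---|---|---|---|---|
| Day 60 visit | 53.5 | 64.2 | 73.1 | 80.3 | 84.8 | 87.5 |
| Discharge | 72.1 | 78.7 | 83.3 | 86.5 | 88.2 | 89.2 |
| Last evaluable start day | 79.2 | 83.4 | 86.1 | 88.0 | 89.1 | 89.6 |

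With the best of the three choices, the Day 15 shortfall at gap 3 is 90.2 − 79.2 = 11.0 points, and at gap 5 it is 90.2 − 86.1 = 4.1. At gaps 6 to 8 it is 2.2 down to 0.6. It does not vanish because leaving care follows improvement in the model, so the censoring is informative.

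**Sensitivity.** The share recorded by Day 30 with gap SD 2 / SD 4 is 62 / 56% at gap 3, 90 / 74% at gap 5 and 99 / 92% at gap 8. With median improvement at Day 10, it runs from 56.5% (gap 3) to 93.6% (gap 8), against a true 96.7%.

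**The case against.** The best case for the plan has four parts.

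**Daily scores may exist after discharge.** The daily rating in Protocol 7.1.3 has no stated end. Section 7.2 measures adverse events daily to Day 60. Section 7.4.1 describes a separate CRF form for targeted symptoms, and says the adverse event form reports significant improvement or worsening of them. Appendices 10 and 13 are not in the text available here. This stands as a reason to check first. It does not remove the point. Section 7.1.3 collects symptoms together with WHO clinical status, which the same section assesses daily only during hospital care and then at visits. A form triggered by significant change is not a daily score of every targeted symptom. No passage links adverse event data to the four-day rule.

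**Hospital care can outlast admission.** Because it includes day-hospital monitoring, the Synopsis wording may keep daily scoring going longer than the Protocol 5.8 wording, which is tied to admission. That is fair, and it is one more reason to reconcile the two.

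**The large percentages need an unfavourable reading.** If a valid assessment means one at which the four-day rule can be evaluated, the Day 30 estimate is already 96-98% at gaps of 3 to 5 days. True, but SAP 9.0 does not say so. The gap, its spread, permanent improvement and the absence of deaths are all assumptions; the sample size example in Protocol 8.1 itself takes 20% control mortality. The model also starts end of care at Day 4, so it leaves out the shortest stays.

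**The trial closed early.** SAP 6.0 rules out formal significance tests, and SAP 11.6 rules out complex outputs and sensitivity analyses. This limits the consequence. However, Table 3 still commits to the curve, and SAP 6.0 expects readers to compare the arms numerically.

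**Conclusion.** The point holds on the schedules as written. Sustained improvement or resolution that starts after discharge, or less than about 3 days before it (about 2 if a visit falls the next day), generally cannot be recorded without readmission. The general rule in SAP 9.0 can then hold those patients at risk as not improved to a late single visit.

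The size is unknown. Under the assumed model with mean gaps of 3 to 5 days, the choice between the Day 60 visit and the last evaluable day moves the Day 30 estimate from about 59-80% to 96-98%, against a true 99%. At longer gaps the difference shrinks to a few points.

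A reader might infer three stronger things that the documents do not support:

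- that the arms are distorted differently, which would need the gap from improvement to end of care to differ by arm, and nothing shows that it does;
- that scoring after discharge certainly did not happen, which cannot be said without Appendix 13 and the CRF;
- that the model percentages estimate the error in this trial, when they only show how sensitive the curve is to an unstated choice.

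The endpoint is a non-key secondary one reported descriptively, so this should be corrected but does not threaten the main conclusions. Confidence is medium because of the unseen appendices.

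**What to change.** 1. Check Appendix 13 and the CRF for daily symptom scoring after discharge. Reconcile the Synopsis, Protocol 5.8 and 7.1.3, and state how the data in 7.2 and 7.4.1 relate to this endpoint, if at all.
2. If there was no such scoring, keep the four-day definition. State in SAP 9.0, and in the footnote to this endpoint in Table 3, that patients without an event are censored at the last day on which the four-day rule could be evaluated, meaning the last day s with scores on s to s+3. State also what is done with patients for whom no such day exists.
3. Footnote the output: improvement around or after discharge is not captured, and a shortfall remains (about 4-11 points at Day 15 in the model above, at gaps of 3 to 5 days).

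The cost is a few sentences of SAP text and a programming rule applied to data already collected. SAP 11.8 already promises estimand details as table footnotes.

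A visit-based supplementary analysis, in which improvement is confirmed at the next scheduled visit, is optional and not part of this fix. It is a different endpoint because it accepts unobserved relapse between visits. It would be specified after the unmasking decision of 19 March 2024 (SAP 8.2) and would need an exception to the limit on outputs in SAP 11.6. Its good performance in a model follows largely from assuming that improvement is permanent.
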